The use of fitness technology services could have beneficial effects on chronic disease management in late life, including positive changes in health perception, social functioning, and mental health (Lindeman et al., 2020). Fitness technology is regarded as a vital means for maintaining and enhancing older people's quality of life (Khosravi et al., 2016; Mitzner et al., 2018). In addition, previous research also indicated that information communication technologies could provide a link between older adults and their informal and formal networks. Technologies allow older adults to transcend spatial barriers and provide them a greater sense of connection to other people (Clarke et al., 2009; Schlomann et al., 2020). Exploring the role of social factors in increasing physical activity using technology is a promising direction (Zhang et al., 2016).

Objectives

This paper reports on the use of WeChat to improve physical and social activity among community dwelling older adults. WeChat is a free mobile text and voice messaging communication service. This pilot study explored the efficacy of one function of the app WeChat: a group-based pedometer function WeRun. There are previous empirical studies conducted on WeRun with younger adults; for example, Gui and colleagues (2017) conducted a qualitative study of 32 users of WeRun. Their findings indicated that sharing fitness data with pre-existing social networks motivated users to continue self-tracking their steps and enhanced their existing social relationships.

However, we are not aware of any empirical studies conducted using WeRun with older adults.

The objectives of this study are to explore: a) whether the participants in the treatment group would show greater increases and higher maintenance of daily steps as well as greater increases in level of social engagement and exercise self-efficacy in comparison to the participants in the control group who were not given the treatment; and b) whether social engagement would be a significant mediator, that is a mechanism of behavior change.

Design

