The study was approved by the University's Institutional Review Board. The clinical trial was registered at the US National Institutes of Health (ClinicalTrials.gov). After the participants were deemed eligible to participate in the study, participants were randomly assigned to one of two conditions: treatment or control. During the 4-week study, participants were blinded to condition. Data collection was also blinded to the experimenters, as the survey and physical activity data were collected through online platforms (Qualtrics and WeRun, respectively).

All participants completed a survey with demographic questions and the self-report outcome measures at pretest. They were asked to use WeRun to track their own daily steps for one week, prior to being assigned to groups. This provided pretest physical activity data and helped participants become familiar with WeChat and syncing the data with their phone. After 4 weeks of using the application, all participants completed the same self-report measures to assess changes in the outcomes of interest. They also completed a follow-up assessment 1 month after the post-test for the same measures.

During the intervention, participants' daily walking steps were recorded by WeRun, and the data were logged by the research assistant every day. The research assistant also recorded each participants' daily ranking and number of social interactions in the treatment condition. Messages were sent by email and WeChat messages to the participants to remind them to carry their phone with them as often as possible during the day and use the application every day. The trained research assistant explained how to use WeChat, WeRun to all participants. Participants in both conditions were asked to use the application every day. A message was sent to remind them to use the application if they had not done so for three consecutive days.

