Sample. As shown in the consort diagram in Figure S1, of the 241 adults who filled out our eligibility questionnaire online, 38 were not eligible, 15 gave up as they had trouble downloading the app, 4 did not meet the age requirement, 4 indicating participating in a walking intervention would be a potential health risk, and 3 could not participate due to travel. One hundred and forty-three potential participants who were eligible did not respond when we notified them that they were eligible. Recruitment took place from October 2018 to March 2019, with primary data collection completed in February 2019, and follow-up data collection completed in March 2019. Those who were

physically active (i.e., who had 7,000 - 10,000 daily steps or above everyday) were not included after the one-week baseline. A total of 60 adults were recruited and randomly assigned to either the control condition ($n = 30$) or the treatment condition ($n = 30$). They completed the study in one of three subgroups, with 20 participants randomly assigned into two groups (10 in treatment group, and 10 in control group) for each subgroup.

Measures

Covariates. Age, gender, education, race, and self-reported health were used as covariates in the analyses because of their expected relationship with the outcome measures. For physical health, the participants were asked “in general would you say your health is?” The response options ranged from 1 (poor) to 5 (excellent) with a higher score indicating better physical health.

The outcome measures were administered at the pretest, posttest and follow up using self-report questionnaires given before and at the completion of week 4 of the pilot study and at the 1 month follow up through an online platforms-Qualtrics.

Daily step counts. Participants' daily steps were recorded by using the WeRun function in WeChat by the end of each day during the 4-week intervention period and at the 1 month follow up. Mean daily steps for pretest week, post-test week and one month follow up week were calculated as the mean number of steps across the 7 days in that week of the study.

Percentage change in mean weekly steps at posttest was calculated as the difference between the mean weekly steps at posttest and pretest divided by the mean weekly steps at pretest. The percentage change in mean weekly steps at the one month

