Statistical analyses of survey measures were done using SPSS. Descriptive information and correlations were computed for all study variables. Changes in daily steps, social engagement and exercise self-efficacy from the pretest to 4 weeks were examined. Repeated measures ANCOVA was used to test for effects of the treatment on mean daily step counts over the intervention period, exercise self-efficacy, and social engagement and to compare treatment and control groups at pretest, posttest, and follow-up using a two condition by three occasions design. All post hoc analyses were performed using Bonferroni corrections controlling the covariates. We conducted a sensitivity analysis without the covariates and the results were the same.

Conditional process modeling was applied using PROCESS in SPSS to test the predicted mediation model. Mediation analyses was based on 1000 bootstrapped samples using Hayes’ PROCESS Macro v3.3 (Hayes & Preacher, 2014), allowing for formal tests of the total, direct, and indirect effects of intervention on percentage of change of mean weekly steps from pre-test to post test. The predictor variable was condition, the mediator variable was change in social engagement, and the outcome was percent change in mean weekly steps from pre-test to post test.

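### Pretest enters the 2 x 3 repeated measures ANCOVA only as an outcome occasion; adding it as a covariate in a supportive model would narrow intervals by about 13% to 5% at assumed pretest-posttest correlations of 0.5 to 0.8

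*Combined protocol and SAP*

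**What the plan says.** The Data Analysis Plan applies repeated measures ANCOVA to mean daily steps, exercise self-efficacy and social engagement, "to compare treatment and control groups at pretest, posttest, and follow-up using a two condition by three occasions design". Post hoc analyses are Bonferroni-corrected and control for the covariates. The one sensitivity analysis removes the covariates; none adds pretest. The plan does not say which term or contrast carries the treatment effect.

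Under Measures, the covariate paragraph reads "Age, gender, education, race, and self-reported health were used as covariates in the analyses". The pretest value of the outcome is not in that list.

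Pretest data exist for every outcome. For steps, "Mean daily steps for pretest week, post-test week and one month follow up week were calculated" as 7-day means. For the scales, "The outcome measures were administered at the pretest, posttest and follow up using self-report questionnaires". The Design section places the step baseline before allocation: "They were asked to use WeRun to track their own daily steps for one week, prior to being assigned to groups". It also places the pretest survey at the start of the study.

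One feature is specific to steps. In the Sample paragraph, people who were "physically active (i.e., who had 7,000 - 10,000 daily steps or above everyday) were not included after the one-week baseline". That is the same week that supplies the pretest step value. No comparable screen applies to the two scales.

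**The concern.** A value measured before randomisation can be used in two ways: subtracted from the later value, as an occasion-by-condition contrast does in effect, or entered as a covariate. Both are valid in a randomised trial. Subtraction fixes the coefficient of pretest at 1, while covariate adjustment estimates it. Unless the true coefficient is close to 1, subtraction carries avoidable noise.

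With 60 participants, 30 per arm, intervals are wide whatever is done. A gain that needs no new data is worth having for objective (a), which asks whether treated participants "would show greater increases and higher maintenance of daily steps" and gain more on the two scales. What is at stake is the width of the reported intervals, not the validity of the planned test.

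**Working it through.** **Inputs.** From the documents: N = 60, 30 per arm (Sample); three occasions (Data Analysis Plan); pretest not a listed covariate (Measures); pretest steps recorded before assignment (Design). Assumed: equal SDs at each occasion, equal correlation between occasions, and r from 0.5 to 0.8. The internal consistencies quoted for the scales (.82 and 0.92) are not pretest-posttest correlations and do not supply r.

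**The plan's own figure.** The plan states no precision figure for this analysis. Its sample size statement (56 participants, ρ = 0.3, power above 80%) names no test and does not reproduce directly: read as a two-sided test with ρ = 0.3, it needs 80 to 85 participants. That is a separate matter and does not enter the interval widths below.

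**1. Variance of the treatment difference at one occasion, in SD² units.**
- Change contrast: (4/N) × 2(1 − r)
- Pretest as covariate: (4/N) × (1 − r²)
- Ratio, covariate to change: (1 − r²) / [2(1 − r)] = (1 + r)/2

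**2. Half-width of the 95% interval**, t × √variance, with 58 df for change and 57 df with the covariate. At r = 0.5 the change contrast gives 2.00 × √(0.0667 × 1.00) = 0.52, and the covariate model gives 2.00 × √(0.0667 × 0.75) = 0.45.

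| r | Variance ratio | Change (SD) | Pretest covariate (SD) | SE reduction, 1 − √ratio | Simulated interval reduction |
|---|---|---|---|---|---|
| 0.5 | 0.75 | 0.52 | 0.45 | 13% | 12.6% |
| 0.6 | 0.80 | 0.46 | 0.41 | 11% | 9.8% |
| 0.7 | 0.85 | 0.40 | 0.37 | 8% | 7.0% |
| 0.8 | 0.90 | 0.33 | 0.31 | 5% | 4.3% |

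The simulated reduction is slightly smaller because it includes the lost degree of freedom and chance pretest imbalance.

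**3. Steps, if the screen cut the pretest range.** Assume bivariate normality and an upper cut at c SD on pretest. With m = φ(c)/Φ(c), the pretest variance shrinks to v = 1 − c·m − m². The change variance becomes (1 − r)²v + 1 − r²; the covariate-adjusted variance stays at 1 − r². Here r is the correlation before exclusion.
- c = +1: m = 0.288, v = 0.630. At r = 0.5 the change-to-covariate ratio is (0.25 × 0.630 + 0.75)/0.75 = 1.21, against 1.33 unscreened. At r = 0.7 it is 1.11, against 1.18.
- c = 0: m = 0.798, v = 0.363. The ratios are 1.12 at r = 0.5 and 1.06 at r = 0.7.
- Simulated intervals are 8.2% (c = +1) to 4.7% (c = 0) narrower at r = 0.5, and 4.3% to 2.2% narrower at r = 0.7.

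**4. Validity.** Simulated rejection under the null, at r = 0.5 and 0.7 with and without a cut, is 0.048 to 0.051 for change, 0.049 to 0.052 with the covariate, and 0.047 to 0.051 for the 2-df interaction.

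**The case against.** The strongest reply is that the planned analysis is already valid, uses pretest through the occasion factor, and compares the groups at each occasion with Bonferroni-corrected post hoc tests. Much of this stands, and it rules out several stronger readings.

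- *Bias.* A reader might infer that leaving pretest out of the covariates, or screening on the baseline week, biases the comparison. The screen is applied to the baseline week, which precedes assignment, so regression to the mean affects both arms alike, and the null rejection rates above are nominal.
- *A power gain over the interaction test.* With d = 2 × 0.3/√(1 − 0.09) = 0.63 (one reading of ρ = 0.3), posttest ANCOVA at alpha .05 has 79/85/92/98% power at r = 0.5/0.6/0.7/0.8. The 2-df interaction has 70/80/91/98% if the effect fully persists or fully vanishes by follow-up. But two occasions would be tested, and at alpha .025 the ANCOVA figures are about 69/77/86/96%. The advantage is gone in that case. If half the effect remains, the interaction has 57/67/80/94% and an advantage survives, but part of it comes from testing a single occasion.
- *Steps gain less than the scales.* This holds only at equal r. Steps at r = 0.5 with a +1 SD cut gain 8.2%, more than a scale at r = 0.7 (7.0%) or 0.8 (4.3%). The screen is also described loosely, with a range of step counts and a daily criterion, and may truncate the weekly mean only weakly.
- *Increase and maintenance cannot be told apart as planned.* The per-occasion post hoc comparisons, and the percentage changes defined separately at posttest and follow-up, already address this.
- *Condition x occasion is the treatment test.* It fits the wording of the objective, but no section designates it. The change contrast serves here only as a benchmark.

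None of this touches the like-for-like comparison with the change contrast, where the variance ratio (1 + r)/2 is below 1 for every r below 1.

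**Conclusion.** The point holds as a modest efficiency gain. Against the pretest-to-posttest change contrast, pretest adjustment cuts the variance by 25% to 10%, and the interval width by about 13% to 5%, at r = 0.5 to 0.8 with 60 participants and no screen. For steps, a screen that truncates pretest between +1 and 0 SD reduces the gain to roughly 8% to 5% at r = 0.5 and 4% to 2% at r = 0.7. All of this rests on assumed correlations, equal SDs and, for steps, an assumed cut; the documents give none of them. The documents do not show which outcome would gain most, and no power gain over the 2-df interaction is claimed once two occasions are tested with a multiplicity correction. The planned analysis remains valid.

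**What to change.** For each outcome, add a model with posttest and follow-up as the outcome occasions and, as predictors, the pretest value of that outcome, condition, occasion, condition x occasion and the covariates already listed. Pretest must not also stay in this model as an outcome occasion: once adjusted for itself, its value is constant. Report the adjusted difference at posttest and at follow-up, each with a 95% confidence interval. If the two differences are tested, apply the Bonferroni correction already planned.

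The cost is one added model per outcome, for example in SPSS MIXED, one degree of freedom and a paragraph of SAP text, with no new data. The downside is timing. Follow-up collection ended in March 2019 and the Data Analysis Plan already reports that results were the same without covariates. The model must therefore be labelled supportive and specified after data collection, and it does not replace the planned analysis.

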Treatment condition: Participants used WeChat for 4 weeks, during which time the steps data were recorded by the WeRun function and downloaded by the research assistants. The participants in the treatment condition could interact with the other group members by sending text messages which were documented by the research assistants. The researchers sent out instructions to check step counts on Monday mornings during the 4-week intervention, for example "Dear all, this is Week 1! please remember to take your phone with you as often as possible during the day and check your step count in WeRun by the end of the day. Please also share your number of steps with your group members. Thank you!" The daily walking steps of the participants in this group were displayed to the group and the participant with the highest daily steps in the group was indicated as the champion each day.

Control condition: Participants only saw their own daily walking steps using WeChat. They did not see other group members' daily steps and did not interact or compare walking steps with other group members. The participants received messages on

Monday mornings during the 4-week intervention to remind them to take their phones as often as possible during the day.

Methods

Participants

Eligibility. Inclusion criteria specified that participants must be 60 or older and fit enough to walk for at least 20 minutes at a time. They also needed to have a smartphone, with either an Android or iPhone system with Internet access. A power analysis (using G*Power 3.1) for the study and analysis design indicated that a total of 56 participants (randomly assigned across two groups) would provide adequate power ($> 80\%$) to detect medium-sized effects ($\rho = 0.3$) at $p < .05$. We recruited 60 participants in the northeast U.S. by posting recruiting posters in community public posting boards, including public libraries, grocery stores and shopping malls. Participants were given two 25-dollar gift cards (one at the pretest and one after the 4-week intervention) as compensation for their participation.

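### Three outcomes are tested for a treatment effect with no order among them, and the Bonferroni rule covers only post hoc analyses, so the chance of at least one false positive is about 11% to 14%, not 5%

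*Combined protocol and SAP*

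**What the plan says.** - **Objectives.** Objective (a) asks whether the treatment group shows "greater increases and higher maintenance of daily steps as well as greater increases in level of social engagement and exercise self-efficacy" than controls. Steps come first in the sentence, but no outcome is called primary. Objective (b) concerns mediation.
- **Data Analysis Plan.** Repeated measures ANCOVA, two conditions by three occasions, is applied to steps, self-efficacy and social engagement. No significance level or testing order is given, and the plan does not say which ANCOVA term decides.
- **Multiplicity.** The only statement is "All post hoc analyses were performed using Bonferroni corrections controlling the covariates".
- **Participants, Eligibility.** "A power analysis (using G*Power 3.1) for the study and analysis design" gave 56 participants for more than 80% power "to detect medium-sized effects" (ρ = 0.3) at p < .05. No outcome is named.
- **Timing.** The document is dated 7/22/2019, and the Sample paragraph says follow-up data collection ended in March 2019. The Data Analysis Plan already reports an outcome of the analysis: "We conducted a sensitivity analysis without the covariates and the results were the same".

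**The concern.** A post hoc correction acts within an outcome, after its main test. It does nothing about having three main tests, any of which could be reported as the treatment working. With no order stated, the error rate for the conclusion that something changed is that of the whole set, not the 5% in the power statement. Because the text was written after data collection and mentions a result, a reader cannot tell from it whether the outcome that leads the report was chosen before or after the data were seen. The power figure has the same gap: it fits one test, and the reader is not told which.

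**Working it through.** **1. The plan's own figure.** Inputs from Eligibility: N = 56, ρ = 0.3, level 0.05. Assumed: the repeated-measures test between two groups over three occasions, with a correlation of 0.5 between occasions (the documents give none).

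- f = 0.3/√(1 − 0.09) = 0.3145
- λ = N·f²·3/(1 + 2 × 0.5) = 56 × 0.0989 × 1.5 = 8.31
- Critical F(1, 54) = 4.02, so power = 80.8%. At N = 54 it is 79.3%.

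So 56 is reproduced as one unadjusted test at 0.05. Occasion correlations of 0.3 to 0.7 would give N from 46 to 66, so this is a plausible route to 56, not a proven one.

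**2. Any false positive among the three main tests.** Inputs: three outcomes (Data Analysis Plan); 0.05 each, two-sided (level inferred from the power statement, sidedness assumed); no true effect on any outcome. The correlations r between outcomes are assumed.

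- Independent: 1 − 0.95³ = 14.3%. Upper bound for any dependence: 3 × 0.05 = 15%.
- Correlated, with a common factor u: 1 − ∫[Φ((1.96 − √r·u)/√(1 − r)) − Φ((−1.96 − √r·u)/√(1 − r))]³ φ(u) du.

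**3. A false result favouring treatment.** Treat each outcome as a directional comparison with upper-tail probability 0.025.

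- Independent: 1 − 0.975³ = 7.3%, against 2.5% for one test.
- Correlated: the same integral with the upper limit only.

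| r | Either direction | Favouring treatment |
|---|---|---|
| 0 | 14.3% | 7.3% |
| 0.3 | 13.6% | 6.8% |
| 0.5 | 12.5% | 6.3% |
| 0.7 | 10.9% | 5.5% |
| 0.9 | 8.4% | 4.2% |

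**4. The planned test itself.** Simulating the condition-by-occasion F-test with 30 per arm (20,000 runs, no covariates) gives 13.9%, 13.6%, 12.6% and 11.2% at r = 0, 0.3, 0.5 and 0.7, in line with the either-direction column.

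**5. Does naming steps first suffice?** With steps at 0.05 and Holm on the two questionnaires, the first Holm step uses 0.05/2 = 0.025.

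- Without a gate, independent: 1 − 0.95 × 0.975² = 9.7%. At r = 0.3, 0.5 and 0.7 it is 9.3%, 8.7% and 7.7%.
- With a gate (questionnaires tested only if steps are significant), a false positive under no effect anywhere requires a false step result, so the rate is 5%. If steps truly respond, Holm holds the two questionnaires at 5%.

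**6. Cost of splitting the level instead.** At 0.05/3 = 0.0167, under the model of step 1, power is 66% with 56 participants and 70% with the 60 recruited. Reaching 80% would need 74.

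**The case against.** The study calls itself a pilot with exploratory aims, and strict error control across outcomes is often not expected of one. This stands, and it limits the severity. It does not remove the point, because the Objectives also speak of efficacy and the sample size is justified by power at p < .05.

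The title concerns physical activity, steps come first in the objectives, and step change is the mediation outcome, so the outcomes are not wholly on a par. This also stands, and it is why steps are the natural lead. But the emphasis is never turned into a testing order. The trial is said to be registered and the registry record was not available here, so the absence of a primary outcome can be asserted of this document only.

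A reader might infer more than the documents support:

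- *That 11% to 14% is the chance of a false claim of benefit.* It counts both directions. For benefit alone the range is 7.3% to 5.5%, still two to three times the 2.5% of one test. A 2-df interaction test also has no single direction, so these directional figures are approximate.
- *That follow-up and mediation push the rate higher.* Follow-up is already one of the three occasions, and post hoc comparisons there fall under the Bonferroni rule. The mediation total effect concerns steps again, and the indirect effect addresses mechanism. In a simulation with no effects (60 participants, 1000 bootstraps, percentile interval, no covariates) the indirect effect was declared in only 0.2% of runs, so it cannot be counted as a further 5% test.
- *That an outcome was picked because it worked.* The text leaves this open; it does not show it.

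**Conclusion.** The point holds. The correction rule leaves the three main tests uncovered and no order is given. The chance of at least one false positive is 14.3% for independent outcomes and 10.9% at a correlation of 0.7 (8.4% at 0.9). For a false result favouring treatment it is 7.3% to 5.5% over correlations 0 to 0.7, against 2.5%.

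These figures rest on four assumptions: the 0.05 in the power statement applies to each ANCOVA; the tests are two-sided; the between-outcome correlations are as tabulated; and no outcome has a true effect. This is a matter of how the conclusions are ordered and reported. It is not a fault in the ANCOVA and does not show that any reported result is false.

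**What to change.** In the Data Analysis Plan:

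1. Base the efficacy conclusion on the planned two-by-three test of mean daily steps at 0.05, and state which term of that model decides.
2. Test social engagement and exercise self-efficacy only if the step test is significant, with Holm adjustment (smaller p against 0.025, larger against 0.05). Without the gate the overall error is still 9.7% for independent outcomes.
3. State that this order was set after data collection and so is not prespecified. A lead outcome named now cannot restore error control by itself. Therefore also report Holm-adjusted p-values across all three outcomes (0.0167, 0.025, 0.05), so that a reader need not rely on the order.
4. Keep maintenance of steps at follow-up as a stated objective. The planned step test already includes that occasion.
5. Say which outcome and which test the figure of 56 refers to.

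Replacing the step test by a pretest-to-posttest contrast is not recommended. It would change the planned analysis, and 56 could not be attached to it without a new calculation.

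The cost is some text and a re-presentation of existing results, with no new data. The downside is a stricter threshold for the two questionnaire outcomes, and no formal claim on either if the step test is not significant.

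### Where a post hoc family holds two or more comparisons, Holm's step-down procedure would give the same familywise error as single-step Bonferroni with equal or better power; the family needs to be named

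*Combined protocol and SAP*

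**What the plan says.** The Data Analysis Plan makes a repeated measures ANCOVA the main test for steps, exercise self-efficacy and social engagement. It is used to "compare treatment and control groups at pretest, posttest, and follow-up using a two condition by three occasions design". On follow-on tests the plan states: "All post hoc analyses were performed using Bonferroni corrections controlling the covariates". It does not mention a step-down version, so the correction is read here as single-step. It does not say which comparisons form a family, or how many there are.

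The Objectives section asks whether the treatment group shows "greater increases and higher maintenance of daily steps", which names both a rise and its persistence. The power statement under Participants (Eligibility) "indicated that a total of 56 participants (randomly assigned across two groups) would provide adequate power". It is set at the .05 level and mentions no multiplicity adjustment. The Sample paragraph reports 30 randomised to each arm.

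**The concern.** A two-by-three omnibus test does not show whether the arms differ at post-test, at follow-up or at both. The post hoc contrasts do that, so their power bears on the two parts of the daily-steps objective.

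Single-step Bonferroni holds each of k comparisons at 0.05/k, even after another member of the family has been rejected. Holm tests the ordered p-values at 0.05/k, 0.05/(k-1), and so on up to 0.05, and stops at the first failure. Its familywise guarantee is the same and needs no added assumption. Where k is 2 or more, a real follow-up difference may therefore be missed more often than error control requires. In a 60-person trial that is worth avoiding when the alternative costs almost nothing.

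**Working it through.** **Inputs from the document.** Alpha is 0.05 (two-sided assumed), the effect is rho = 0.3, the planned total is 56, the actual allocation is 30 per arm, and there are three occasions.

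**Assumed, because the document does not give them.** These are the family size k, the correlation between occasions, and the effect at follow-up.

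**1. The plan's own figure.**
- f = 0.3/sqrt(1 - 0.09) = 0.3145, so d = 2f = 0.629 and f² = 0.09/0.91 = 0.0989.
- For the between-group effect over m = 3 occasions with assumed correlation r = 0.5, lambda = N × f² × m/(1 + (m - 1)r) = 56 × 0.0989 × 3/2 = 8.31.
- Power is 80.8% on 1 and 54 degrees of freedom. The smallest N reaching 80% is 55, or 56 with equal arms.

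The stated 56 is therefore reproducible under that assumed correlation. It refers to an unadjusted test and does not involve the post hoc correction.

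**2. Thresholds.**

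| k | Bonferroni, every comparison | Holm, smallest p to largest |
|---|---|---|
| 1 | 0.05 | 0.05 |
| 2 | 0.025 | 0.025, 0.05 |
| 3 | 0.0167 | 0.0167, 0.025, 0.05 |

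At k = 1 the methods are identical. At k = 2, showing both differences needs both p-values at or below 0.025 under Bonferroni. Under Holm it needs the smaller at or below 0.025 and the larger at or below 0.05.

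**3. Arm contrasts at the three occasions as one family (k = 3).** Simulation with 30 per arm, normal outcomes, a t test at each occasion, no difference at pretest, correlation 0.6 to 0.8, and 40,000 trials per setting:

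| Difference in SD, post-test / follow-up | Quantity | Bonferroni | Holm |
|---|---|---|---|
| 0.63 / 0.63 (planned effect) | both shown | 34-39% | 40-45% |
| 0.63 / 0.63 | follow-up shown | about 49% | about 52% |
| 0.7 / 0.7 | both shown | 45-50% | 52-56% |
| 0.8 / 0.6 | follow-up shown | 44-45% | 50% |
| 0.63 / 0.3 (effect decays) | follow-up shown | about 10% | about 13% |

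Familywise error under the full null is about 3.5-4.3% and identical for the two methods. With real later effects, Holm's is 3.2-3.7%. No simulated trial lost a rejection under Holm, and the chance of at least one rejection was the same.

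**4. Contrasts of change from pretest.** This separate simulation allows for the five covariates in the degrees of freedom (60 - 2 - 5 = 53) and assumes correlation 0.5 between the test statistics. At d = 0.63 for both changes, showing both rises from 38.6% to 50.0% at k = 2. It rises from 32.0% to 38.4% at k = 3, where the post-test to follow-up contrast is added.

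**5. Occasions compared within one arm (k = 3).** With n = 30, correlation 0.6 and an assumed 0.5 SD change that is sustained, showing both changes rises from 55% to 62%.

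**The case against.** The strongest objection is that the document fixes no family. With only two arms, a correction applied separately at each occasion covers one contrast. Then k = 1 and nothing is lost. This stands. A reader might infer that the plan certainly gives away power, but the text does not support that. The loss is conditional on k of 2 or more, and its size rests on assumptions.

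Second, no passage makes significance at both later occasions a criterion of success, and Holm leaves the chance of at least one rejection unchanged. This also stands. Power for both is only one summary, and the gain for follow-up alone is smaller: 3 points at the planned effect, and about 3 points if the effect decays to 0.3 SD. The larger gain of about 5 points for follow-up assumes 0.8 SD at post-test, which exceeds the planned effect.

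Third, timing. The document is dated 7/22/2019, data collection ended in March 2019, and the Data Analysis Plan already reports a sensitivity result. Choosing a more liberal procedure now would be a data-aware change, and Holm's guarantee presumes that the method was not picked after seeing the p-values. This stands and shapes the fix.

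Fourth, Bonferroni is valid and conservative, yields simultaneous intervals that match its decisions, and may be reasonable in an exploratory pilot. This is true, and it makes the point a refinement. It does not remove the dominance of Holm for decisions in families of two or more.

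**Conclusion.** The point holds conditionally, as a minor improvement. For any post hoc family with k of 2 or more, Holm keeps the same familywise error and is never less powerful. At the planned effect with k = 3, the gain is about 6 points for showing both later differences (34-39% to 40-45%) and about 3 points for follow-up alone (49% to 52%). The direction depends on nothing but k being at least 2. The size depends on the assumed k, the correlation and a follow-up effect equal to that at post-test. The simulation behind those figures also uses t tests at each occasion and leaves out the covariates.

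A reader might go further and conclude that the correction is wrong, that the trial's error control fails, or that the sample size is undermined. None of these follows. Bonferroni controls the error, the omnibus ANCOVA is a separate test, and the calculation of 56 does not use the post hoc correction.

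**What to change.** In the Data Analysis Plan:

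1. Name the post hoc family for each outcome, for example the treatment-control contrasts at post-test and at follow-up. This comes first, because it decides whether any correction applies. Narrowing the family also changes power under either method, so that effect should not be credited to Holm.
2. Replace Bonferroni corrections with Holm step-down Bonferroni corrections within that family. Take the unadjusted p-values from the SPSS comparisons, sort them, and compare them with 0.05/k, 0.05/(k-1), up to 0.05.
3. For this dataset, label any Holm results as post hoc and keep the Bonferroni results beside them. A later trial that reuses the plan can prespecify Holm.

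The cost is a sentence defining the family, a small change of wording and a sort of p-values, with no new data or participants. The one small drawback is that Bonferroni simultaneous intervals, if still printed, may not agree with every Holm decision, and a note should say so.
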